Once a patient is consented, she will be randomly assigned to one of the 2 arms of the study: the eligible women will be randomized to use of a 2% chlorhexidine gluconate (CHG) cloth or placebo cloth (a fragrance free cleansing cloth). Participants will be blinded to the arm in which they have been assigned.

b) Inclusion and Exclusion Criteria

The study will be offered to women at > 24 weeks gestation who are scheduled for a primary or repeat cesarean section. Exclusion criteria include allergy to chlorhexidine unplanned or emergency cesarean section.

c) Number of Subjects

We aim to enroll 1356 participants, 678 patients in each group. About 1800 deliveries by cesarean section occur each year at Mount Sinai. Of these, approximately 1000 are scheduled cesarean sections. Based on our rate of SSI (6%) and the objective of a 67% decrease in SSI rates and expected rate of eligible patients who do not consent at 10%, we plan to enroll 1356 patients in total to account for drop-outs or non-compliance. This number was modified last year based on our sponsor monitoring report in order to account for patients who delivered early or forgot to complete the pre-op wipe treatment. We currently have 1,338 enrolled and need 18 more for recruitment completion.

d) Study Timelines

After informed consent has been obtained, the duration of the subject participation will occur from the time they present for preoperative admission

	Protocol Name:	A randomized trial to determine if a pre-operative wash with a chlorhexidine cloth reduces infectious morbidity in patients undergoing cesarean section
	Principal Investigator/Contact Info:	[name]/[contact] or [name]
	Primary Contact Name/Contact Info:	[name] /[contact] or [name]
	Date Revised:	July 31, 2019
	Study Number:	GCO#14-1410

testing until 6 weeks post procedure. We expect to complete enrollment by September 1, 2019 and complete data analysis by November 1, 2019.

e) Endpoints

The primary outcome will be SSI and postpartum endometritis. Secondary outcomes include other maternal complications or interventions, neonatal ICU admissions, maternal length of stay or readmissions.

f) Procedures Involved in the Human Research

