This study intends to evaluate the effectiveness of a chlorhexidine gluconate (CHG) shower in reducing SSI in patients undergoing cesarean section. Patients will be randomized to one of two groups: administration of a 2% CHG cloth at home on the night before and approximately 3 hours prior to cesarean delivery on the morning of the surgery or cloth with the placebo (commercial cleansing cloth). Patients will receive a phone call, text message, and/or email reminder to apply the wipes (method of PrepCheck reminder will be decided by the patient). Currently, there is no wash or cloth used prior to cesarean section as a standard of care.

Sage Products Inc will be blinding the study groups. The study team will be provided with pre-prepared packages that contain a 4 digit number indicating the product. Only Sage Products Inc will know which number indicates which group. Patients, recruiters, and statisticians will all be blinded. Once data has been analyzed, Sage Products Inc will inform the study teams as to which packages contain the CHG product number and which contain the placebo.

Each patient will be assigned a unique identification code. The code will be linked to the name and date of birth in an encrypted password-protected linking key code file which will be stored on the PI's personal network folder in the Hospital IT server, accessible by the PI only. The data will be stored in a separate password-protected database by the unique identification code. The database will be stored on a secure desktop at Mount Sinai hospital.

There is minimal risk associated with the use of CHG in a surgical setting. Use of CHG in surgery has been well described in the literature as safe with minimal risks. Enrollment in this study does not place a patient at increased risk over other patients undergoing a cesarean section. The only potential unforeseeable and minimal risk is an allergic reaction to the chlorhexidine gluconate.

	Protocol Name:	A randomized trial to determine if a pre-operative wash with a chlorhexidine cloth reduces infectious morbidity in patients undergoing cesarean section
	Principal Investigator/Contact Info:	[name]/[contact] or [name]
	Primary Contact Name/Contact Info:	[name] /[contact] or [name]
	Date Revised:	July 31, 2019
	Study Number:	GCO#14-1410

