Data collected will include demographic variables such as age, parity, BMI, race will be collected, as well as gestational age, number of previous cesarean sections, time from incision to delivery, type of anesthetic, and type of wound closure. Maternal outcomes including EBL, length of incision to delivery, length of operation, type of skin closure, type and use of prophylactic antibiotics, type of skin incision, type of skin closure, indication for cesarean, number of prior cesarean sections, and parity. Charts will be reviewed through the 6 week post partum visit in order to determine how well the skin at the incision site is healing. If patients do not visit Mount Sinai Medical Center for their 2 week wound check, they will be called and asked the following questions: Were you treated for wound infection? Did you experience wound separation or any other wound complications?

g) Specimen Banking

N/A

h) Data Management and Confidentiality

No specimens will be sent out or received in this trial.

All data is de-identified; patients are followed by subject number. Identifiable patient information (consent forms & consent documentation) are kept separately from any data collected. All consent documentation is stored in a locked cabinet at [name]. Identifiable enrollment statistics are kept in a password-protected computer (Excel) spreadsheet that is only accessible by members of the research team on a departmental J Drive.

Data will be analyzed on an intention to treat basis. Statistical analysis will be performed by SAS using X 2 test or Fisher exact test (categorical variables) and student t test or Mann-Whitney U test (continuous variables). Statistical significance will be set at p<0.05.

i) Provisions to Monitor the Data to Ensure the Safety of Subjects

Part I: Elements of a Data and Safety Monitoring Plan

MSSM Principal Monitor:

The principal monitor for this study is the PI:

Last Name: [name]

First Name: [name]

Academic Title: Professor

Department: OB/GYN – Maternal Fetal Medicine

Mailing Address: [REDACTED]

[contact]

	Protocol Name:	A randomized trial to determine if a pre-operative wash with a chlorhexidine cloth reduces infectious morbidity in patients undergoing cesarean section
	Principal Investigator/Contact Info:	[name]/[contact] or [name]
	Primary Contact Name/Contact Info:	[name] /[contact] or [name]
	Date Revised:	July 31, 2019
	Study Number:	GCO#14-1410

[contact]

E-mail: [contact]

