	Protocol Name:	A randomized trial to determine if a pre-operative wash with a chlorhexidine cloth reduces infectious morbidity in patients undergoing cesarean section
	Principal Investigator/Contact Info:	[name]/[contact] or [name]
	Primary Contact Name/Contact Info:	[name] /[contact] or [name]
	Date Revised:	July 31, 2019
	Study Number:	GCO#14-1410

7) Provisions for Research Related Harm/Injury

The patients will receive standard obstetric care and have access to the obstetric staff (physicians, nursing) as well as all of the resources on the labor floor including the use of the ORs, blood bank, continuous fetal monitoring. Any potential adverse events are inherent to the operative delivery itself and regardless of the study. Any complications that occur during cesarean section will be managed by the obstetricians and anesthesiologists. As standard of care, a physician is present during a cesarean section and is experience in managing complications. The patient is billed as per standard scheduled cesarean section regardless of complications due to the surgery.

8) Potential Benefits to Subjects

Direct benefit to subject is unknown. However, the potential benefit is that we may find a reduction in infectious morbidity related to the cesarean section surgery.

9) Provisions to Protect the Privacy Interests of Subjects

The patients will be approached by the nurse during pre-operative appointment to determine if they are willing to be included for randomization. Their participation will not require any additional examinations. All research-related discussions will be held in a private location. Any questions will be answered and fully discussed to maximize patient comfort. If they choose to participate they will be randomized and receive care within the accepted standards. If a patient must be called to find out how the wound is healing, the research team members placing the class will not leave a message or speak to anyone except the patient herself. When called, she will be asked if she can discuss the research study at that time, ensuring patient privacy and comfort.

10) Economic Impact on Subjects

There are no foreseeable costs that subjects may incur through participation in the research.

11) Payments to Subjects

There will be no payment to subjects.

12) Consent Process

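### The only active follow-up call asks about the wound alone, so endometritis treated elsewhere, and late infection treated elsewhere in women with no 6-week record, are not sought

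*Combined protocol and SAP*

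**What the plan says.** All references are to the combined protocol and SAP.

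- **Outcome (5e, Endpoints):** "The primary outcome will be SSI and postpartum endometritis".
- **Duration (5d, Study Timelines):** participation runs "until 6 weeks post procedure".
- **Passive follow-up (5f, Procedures):** "Charts will be reviewed through the 6 week post partum visit". The stated purpose is to see how the skin at the incision is healing.
- **Active follow-up (5f):** "If patients do not visit Mount Sinai Medical Center for their 2 week wound check, they will be called". The call has two questions: "Were you treated for wound infection? Did you experience wound separation or any other wound complications". Its date is not given. A missed 6-week visit triggers no contact.
- **Conduct of the call (section 9, Privacy):** the caller "will not leave a message or speak to anyone except the patient herself". The call is again described as being about wound healing.
- **Analysis (5h, Data Management):** "Data will be analyzed on an intention to treat basis". The tests and the 0.05 level follow. There is no rule for a woman whose outcome was not ascertained to 6 weeks.
- **Blinding (5f):** "Patients, recruiters, and statisticians will all be blinded".
- **Size and status (5c, Number of Subjects):** 1,356 women, 678 per arm, a total said to allow for drop-outs and non-compliance; 1,338 are enrolled.

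**The concern.** Endometritis is a named part of the primary outcome, but it is an infection of the uterus and neither call question reaches it. The catch-all at the end of the second question is limited to the wound. A woman who missed the 2-week check, was treated for endometritis at another facility and answered the call truthfully could be recorded as having no infection.

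The second gap is one of timing. Follow-up is meant to last 6 weeks, but active contact hangs on the 2-week check. A woman seen or called at about that time, treated elsewhere for any infection later, and without a 6-week record is not asked again.

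What is at stake is the completeness of the primary event count, and so the absolute risks, the risk difference and some power. Intention to treat fixes the arm in which a woman is analysed. It does not say how an unascertained outcome is counted.

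**Working it through.** **1. Routes by which an event can be found**

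| Situation | Wound infection | Endometritis |
|---|---|---|
| Treated at the hospital | in the chart | in the chart, if abstracted |
| Treated elsewhere, woman has a 6-week visit | may be noted there | may be noted there, if abstracted |
| Treated elsewhere before the call, woman only called, no 6-week record | asked | **not asked** |
| Treated elsewhere after the 2-week check or call, no 6-week record | **not sought** | **not sought** |

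The gap is confined to the cells in bold.

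**2. The plan's own sample size**

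Inputs from sections 4 and 5c are a 6% control risk, a 67% reduction (0.06 × 0.33 = 1.98%) and a 10% allowance. Power and sidedness are not stated. With two-sided 0.05, the pooled-variance formula and an assumed 95% power, 614 per arm are needed. Then 614/0.9 = 682.2, rounded up to 683, which is the section 4 figure. Section 5c gives 678, so 678 − 614 = 64 per arm is margin under that reading.

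**3. Effect of missed events**

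The documents give no miss rate, so the following is assumed. Let u be the share of women with no 6-week record and f the share of their events that is missed, the same in both arms, with the same event risk with or without a record. The share of events lost is m = u × f. With u and f each between 0.10 and 0.50, m runs from 0.01 to 0.25.

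Observed risks are 0.06(1 − m) and 0.0198(1 − m). Their ratio is 0.0198/0.06 = 0.33 for every m. The difference is 4.02(1 − m) points.

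Power = Φ{[d√n − 1.96√(2p̄(1 − p̄))] / √[p₁(1 − p₁) + p₂(1 − p₂)]}, where d = p₁ − p₂, p̄ is the mean of the two risks and n = 678. With m = 0: d√n = 0.0402 × √678 = 1.0467, p̄ = 0.0399, and (1.0467 − 1.96 × 0.2768)/0.2753 = 1.83, so power is 96.6%.

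| Events missed | Risks | Difference (points) | Expected events | Power |
|---|---|---|---|---|
| 0% | 6.00% vs 1.98% | 4.02 | 54.1 | 96.6% |
| 1% | 5.94% vs 1.96% | 3.98 | 53.6 | 96.5% |
| 10% | 5.40% vs 1.78% | 3.62 | 48.7 | 94.8% |
| 15% | 5.10% vs 1.68% | 3.42 | 46.0 | 93.6% |
| 25% | 4.50% vs 1.49% | 3.02 | 40.6 | 90.4% |

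**4. How unascertained women are counted**

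- *No recorded event counted as no event, everyone kept:* the table above. Risks are understated by the factor (1 − m) and the ratio is preserved.
- *Only women with complete 6-week ascertainment:* under the same assumptions the risks are the true 6.00% and 1.98%, but n falls to 678(1 − u). Power is 94.9% at u = 0.10 and 88.7% at u = 0.30.
- *Incompletely followed women dropped unless they have a recorded event:* risk = p(1 − uf)/[(1 − u) + u(1 − f)p]. At u = 0.50, f = 0.10, p = 0.06 this is 0.057/0.527 = 10.82%, against a true 6.00%. This hybrid should be avoided.

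**5. Who can still be reached**

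1,356 − 1,338 = 18 women, or 18/1,356 = 1.3%, plus women within 6 weeks of surgery. At the document date those are women operated on after 31 July − 42 days = 19 June 2019. A 6-week call falls by the planned 1 November end of analysis only for surgery on or before 1 November − 42 days = 20 September, which is 19 days after the planned end of enrolment.

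**The case against.** The strongest reply is that little harm to the primary comparison can be shown. Every miss rate above is assumed. Power stays at 90.4% or more across the range and the risk ratio does not move. The total was already enlarged for drop-outs and non-compliance. If the 6% planning rate itself leaves out infections treated elsewhere, there is no loss against plan. All of this stands, and it is why the point is minor.

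The text also leaves room for better capture than the worst reading. Section 5f speaks of charts without limiting them to the hospital's own. A 6-week visit may record outside treatment. The undated call could be late enough to catch later wound infections. These narrow the gap but do not close it: however late the call, its questions do not ask about endometritis. The missing counting rule, taken alone, is missing detail.

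A reader might infer two stronger things. One is that the trial is biased toward one arm. The documents do not support that: patients, recruiters and statisticians are blinded, and bias would need follow-up or capture to differ by arm, which nothing suggests. The other is that endometritis is not being collected at all. That does not follow either. It is a named primary outcome, and chart review through 6 weeks could record it. The stated purpose of that review is the incision, which is a reason to confirm what was abstracted and no proof that it was omitted.

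**Conclusion.** The point holds as a minor one. The call script does not match the primary outcome. Endometritis treated elsewhere in a woman who was only called, and infection treated elsewhere after the 2-week check or call in a woman with no 6-week record, are not sought by the procedures as written.

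The expected consequence is understated absolute risks and a smaller risk difference, with a modest loss of power and an essentially unchanged risk ratio. The size depends on the assumed 1–25% of events missed, on equal loss in both arms, and on the planning risks of 6% and 1.98% with a two-sided test. Unequal loss would change the conclusion, but nothing in the documents points to it.

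**What to change.** 1. **Call script (5f).** Add a question on treatment for uterine infection or endometritis at any facility. Use it for the 18 women still to be enrolled and for those still within 6 weeks of surgery, and make the same call at about 6 weeks to any of these women with no 6-week record. Open-ended re-contact of women long past 6 weeks is not advised: recall would be poor.
2. **Chart abstraction (5f).** State that it covers surgical site infection and endometritis through 6 weeks. Confirm that endometritis was extracted for women already followed, before the key codes are erased as section 6 provides.
3. **Analysis (5h), before the package codes are disclosed.** Keep all randomised women in the primary analysis, with no recorded event counted as no event. Report by arm the number without 6-week ascertainment. Add one sensitivity analysis limited to women with complete 6-week ascertainment, leaving out incompletely followed women whether or not they have a recorded event.

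**Cost.** One extra question, a few extra calls and one added table. The reach of item 1 is small, because 1,338 of 1,356 women are already enrolled. The last calls may press on the 1 November 2019 analysis date, particularly as section 5a allows recruitment at a BPP visit whose timing before surgery is not stated. Items 2 and 3 need no patient contact and apply to the whole trial.

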[name] has years of experience in research and clinical practice and is qualified to serve as the principal monitor to ensure the safety of participants. All adverse events, subject compliance with the protocol, drop outs, and all study data will be closely monitored and reviewed on an annual basis.

Standard of care and labor floor protocol will be followed in order to ensure standard of care for all cesarean sections.

If there is a temporary or permanent suspension of the study, in addition to the PPHS, the FDA and clinicaltrials.org will be notified.

j) Withdrawal of Subjects

There are no anticipated circumstances under which subjects will be withdrawn from the research without their consent.

6) Risks to Subjects

The risks to subjects are inherent to the cesarean section process itself outside of the study. The only difference in care is use of chlorhexidine gluconate in one arm of the study. This may result in a decreased rate of infection morbidity.

If used as instructed, the only potential unforeseeable risk is an allergic reaction to the chlorhexidine gluconate. Allergic reaction could include itching or hives, swelling in your face or hands, swelling or tingling in your mouth or throat, chest tightness, and/or trouble breathing.

The patients in our study are all scheduled for cesarean section by the patient’s physician. The inherent nature of cesarean section requires an abdominal surgery. As standard of care, all women in this study will be provided with analgesia. In addition, enrollment in this study will not alter the current strategies regarding cesarean section.

There is always the risk of loss of confidentiality; however, there are procedures in place to minimize this risk. To ensure confidentiality, the following system will be adhered to: When subjects are enrolled in this study, they will be assigned a unique identification code. Corresponding medical record numbers for each code (key code) will be stored in a password locked document on the MFM server that can be accessed only by members of the research team. At the conclusion of the data extraction, the outcome variable will be assessed and the key codes to the medical record numbers will no longer be necessary and that information will be permanently erased from the key code file. Electronic data with identifiers will be encrypted according to Data Security Standards.

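### Do the two accounts of the linking key in 5f and Section 6, and the silence on identifying one woman's product, call for a change to the plan?

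*Combined protocol and SAP*

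**What the plan says.** Section 5f (Procedures Involved in the Human Research) says of the study code: "The code will be linked to the name and date of birth in an encrypted password-protected linking key code file". That file sits in the principal investigator's "personal network folder in the Hospital IT server, accessible by the PI only". The study data are kept in a separate database under the code. Section 5f gives no rule for destroying the key.

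Section 6 (Risks to Subjects) describes a key that pairs each code with a medical record number, held "in a password locked document on the MFM server that can be accessed only by members of the research team". It continues: "At the conclusion of the data extraction, the outcome variable will be assessed". The link to record numbers is then said to be no longer needed, and "that information will be permanently erased from the key code file".

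Section 5h (Data Management and Confidentiality) mentions a further identifiable item, a password-protected enrolment spreadsheet on a departmental drive open to the research team.

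On product identity, Section 5f says that the study team receives "pre-prepared packages that contain a 4 digit number indicating the product". It adds: "Only Sage Products Inc will know which number indicates which group". After the analysis the supplier tells the study teams "which packages contain the CHG product number and which contain the placebo". No earlier disclosure for a single participant is described.

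**The concern.** Section 6 offers the erasure as part of its system for protecting confidentiality. If there are two files, erasing record numbers from one leaves the other still tying the code to a name and date of birth, with no end date. If there is one file, the protocol contradicts itself on what it holds, where it is and who may open it. Either way, a reader cannot tell how long a woman's study data remain traceable to her.

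The second worry concerns blinding. The protocol names allergic reaction to chlorhexidine as the study-specific risk, so the question of what one woman received could arise before the analysis. The supplied text gives no route to an answer. Nor does it say whether the 4-digit numbers are unique to a package or shared within an arm. If they are shared, an answer about one woman would reveal the assignment of others. If that reached people who judge wound outcomes, blinding would suffer.

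**Working it through.** No error rate, power or sample-size figure is involved, so the check is a comparison of texts followed by a trace of which links the analysis needs.

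**Step 1. The two accounts side by side.**

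| Attribute | Section 5f | Section 6 |
|---|---|---|
| Identifier tied to code | Name and date of birth | Medical record number |
| Location | Principal investigator's folder, hospital server | MFM server |
| Access | Principal investigator alone | Research team |
| Erasure | Not mentioned | Record-number link, after extraction |

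The first three rows conflict if one file is meant. The fourth is a statement against a silence, which is a gap and not a contradiction.

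**Step 2. One file or two?** Both sections use the term key code file, which favours one file described twice. Two files are also plausible: Section 5f has charts reviewed to the 6-week visit and women telephoned if they miss the 2-week wound check, which is hard to run from a file only the principal investigator can open. The text does not settle it. With one file, erasing the key codes may sever name and date of birth too. With two, Section 6 still does what it promises, because it commits only to removing the record-number link and does not promise full anonymisation.

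**Step 3. Does the key enter the comparison of arms?** The analysis needs outcome by study code, study code to package number, and package number to arm. None of these uses name, date of birth or record number once outcomes have been extracted. Section 6 places outcome assessment before it calls the link unnecessary, so erasure as written does not cut off outcome collection. The intention-to-treat comparison in Section 5h is the same whether the key is kept, erased or held in two places.

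**Step 4. The chain from participant to product.**
- Participant to study code: described, in two versions.
- Study code to package number: not described, but an analysis by arm cannot be run without it.
- Package number to product: known to the supplier, with disclosure described only after analysis.

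Nothing in the text prevents the supplier from answering a question about one package. Consent pages are absent from the supplied text and may have carried an instruction. On the numbering, the Section 5f wording leans towards a number shared by an arm, but this is not stated, and several numbers per arm is also possible.

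**Step 5. Counts.** Section 5c gives 1,338 enrolled of 1,356 planned: 1,338 / 1,356 = 98.7%. Remaining: 1,356 − 1,338 = 18, and 18 / 1,356 = 1.3%. With the total of 1,365 in Section 4, the enrolled share is 1,338 / 1,365 = 98.0%. These are numbers of women covered by the descriptions. The documents give no reaction rate, so how often a product would need to be identified cannot be estimated.

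**The case for a change.** The strongest case for acting is that the conflict over the key is real and is not removed by supposing one file. In that case identifier, location and access still disagree, and the erasure sentence names only record numbers. Confidentiality is a commitment to women already enrolled, and one agreed account would cost a few sentences. On the product, a trial that names allergic reaction as its particular risk would normally set down how to learn a participant's assignment and who may be told.

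The textual conflict stands, and so does the observation that no individual route is described. Three further claims do not:
- That erasure definitely misses the name link assumes two files, which the text leaves open.
- That outcomes are judged only when extraction ends is not what Section 6 says, and Section 5f has wound information gathered during follow-up.
- That one answer would unblind the trial rests on shared numbering, which is not stated, and on the answer reaching outcome assessors, which nothing in the text implies.

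**Conclusion.** The inconsistency is genuine but clerical: three conflicting attributes and one silence about where a linking file sits, who opens it and when it ends. It is a matter of data custody that the investigator can settle without touching the randomization, endpoints or analysis. The missing route to one participant's product is an operational gap that a study team and supplier can fill when needed.

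The effect on the estimated difference between arms, its p-value and the trial's conclusion is nil on the plan as written. This rests on three assumptions: package number was recorded against study code, as any analysis by arm requires; outcomes were assessed before erasure, as Section 6 orders it; and no product identity reached outcome assessors early, which the documents give no reason to doubt. Writing down a file description, an erasure scope and an unblinding procedure would tidy the document but would not improve the evidence. No change to the plan follows.
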